**** Used to determine whether new biomedical or behavioral interventions are safe, efficacious, and effective.***

Drugs / Biologics	No
* Drugs / Biologics That Are Not a Part of Standard Practice * Controlled Substances	
* Drugs / Biologics Supplied by the Research Sponsor or Purchased with Study Funds	
Radiological Procedures	No
Hazardous Materials	No
* Recombinant DNA * Viral Vectors * Plasmids * Bacterial Artificial Chromosomes * Toxic Chemicals, Potentially Toxic Medications, Carcinogens * Autologous Cell Lines	
Request Use of Clinical Research Unit Resources	No

3. Summary - Background

Objectives

To test the hypothesis that patients undergoing ECV with spinal anesthesia will have the same rate of success as those undergoing the procedure without anesthesia initially with reattempting using spinal if unsuccessful.

Background

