The primary outcome will be the success rate of external cephalic version to cephalic presentation. Secondary outcomes will include: time from procedure to delivery, mode of delivery, patient discomfort, adverse events during procedure (ie.fetal bradycardia, emergent cesarean section, abruption), neonatal outcomes (ie. birthweight, Apgars, cord pH, NICU admission). The external cephalic version procedure may be terminated in any patient at any time regardless of this study in the event of persistent fetal heart rate abnormalities, maternal request, or any other adverse findings that the physician believes is an indication that the procedure must be terminated.

Protocol Was Already Approved by the Icahn School of Medicine at Mount Sinai (ISMMS) Institutional Review Board (IRB) Under a Different Principal Investigator No

Protocol Was Previously Submitted to an External(non-ISMMS) IRB No

4. Research Personnel

Name/Department	Role/Status	Contact	Access	Signature Authority	Phone	Email
[name] / Obstetrics/ Gynecology	PI /	Yes	SIGNAUTH			
[name] / Obstetrics/ Gynecology	Co-Investigator /		EDIT			
[name] / Obstetrics/ Gynecology	Co-Investigator /		EDIT			
[name] / Obstetrics/ Gynecology	Co-Investigator /		EDIT			
[name] / Obstetrics/ Gynecology	Co-Investigator /		EDIT			
[name] / Anesthesiology	Co-Investigator /		EDIT			
[name] / Anesthesiology	Co-Investigator /		EDIT			
[name] / Anesthesiology	Co-Investigator /		EDIT			

5. Sites

Site Name Mount Sinai West

Other External Site Name

Contact Details

Approved 0

Approval Document

Funded By Mount Sinai 1

Reviewed By Mount Sinai IRB

Other IRB

6. Subjects - Enrollment

Site Name	Mount Sinai Roosevelt
Subjects To Be Enrolled	
100	
Total	100

7. Subjects - Setting and Resources

Setting of Human Research Other

Specify Other Setting of Human Research

Labor and Delivery unit at Mount Sinai West hospital.

Total Number of Subjects Needed 100
To Complete Study

Feasibility of Meeting Recruitment Goals

From 2012-present we have attempted approximately 89-115 external cephalic versions a year. Each year we have been increasing in numbers, with 115 patients in 2015. These numbers only include patients who had an attempted ECV and does not include patients that were scheduled for ECV but the procedure was not performed for various circumstances. Given this information we believe that it will take approximately 1-2 years to recruit 100 patients.

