There is no anticipated research related harm for study subjects. There is a very small risk of adverse outcomes inherent in the procedures themselves, but this is not due to participating in research. Medical personal will be readily available for any adverse outcome as is standard for all pregnant patients in such events.

Expected Direct Benefit to Subjects

Each subject may be expected to directly benefit from participation in this study. For those that are in the immediate spinal group, these patients may benefit from less discomfort (as is noted in prior studies) and an increased external cephalic version success rate (compared to controls). Those who are in the spinal anesthesia only if ECV fails without it, may benefit from not having to undergo an additional procedure (neuraxial anesthesia) when attempt leads to cephalic presentation with ease. It is unclear if these patients will have the same ECV success rate, but prior non-randomized trials do suggest this finding.

Benefit to Society

The results of this study may benefit society in that a better protocol may be in place for ECV attempts that increases the rates of success without increasing the rate of risk or cost.

Provisions to Protect the Privacy Interests of Subjects

The patients will be approached by the a member of the study team on the labor floor to determine if they are willing to be included in the study. Their participation will not require any additional examinations. They will only be approached once by the study team on the labor floor to determine if they are willing to participate. All research-related discussions will be held in the patient's private room. Any questions will be answered and fully discussed to maximize patient comfort. Patients will be allowed time to consider participation and we will explain to patients that we will follow up their delivery information, but will not contact them directly. We will also assure the patient all the steps that will be taken to protect their privacy.

Economic Impact on Subjects

We do not see any foreseeable additional costs to subjects for participating in this research study. The patient is already in the hospital to undergo a version and anesthesia may or may not be used for this procedure even when not participating in the study.

11. Subjects - Pregnant Women

**Preclinical Studies Including Those No
on Pregnant Animals and Clinical
Studies Including Those on Non-
Pregnant Women Have Been
Conducted**

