Accessing Data Yes

Receipt or Transmission of Data Yes

Holding Code That Can Be Linked to Identity of Participants No

Research Personnel Responsible for: [name]

Accessing Data Yes

Receipt or Transmission of Data Yes

Holding Code That Can Be Linked to Identity of Participants No

Research Personnel Responsible for: [name]

Accessing Data Yes

Receipt or Transmission of Data Yes

Holding Code That Can Be Linked to Identity of Participants No

Research Personnel Responsible for: [name]

Accessing Data Yes

Receipt or Transmission of Data Yes

Holding Code That Can Be Linked to Identity of Participants No

Research Personnel Responsible for: [name]

Accessing Data Yes

Receipt or Transmission of Data Yes

Holding Code That Can Be Linked to Identity of Participants No

Research Personnel Responsible for: [name]

Accessing Data Yes

Receipt or Transmission of Data Yes

Holding Code That Can Be Linked to Identity of Participants No

Research Personnel Responsible for: [name]

Accessing Data	Yes
Receipt or Transmission of Data	Yes
Holding Code That Can Be Linked to Identity of Participants	No

Duration Data Will Be Stored

Data will be stored until the data is analyzed, within 1 year from study completion.

Steps That Will Be Taken to Secure the Data During Storage, Use, and Transmission

The study investigators will collect medical information about the subject over the course of the study. Study data will be entered into a de-identified research database, using a unique code numbering system. A code number linked to subject identity will be used instead of names. The code number will not be derived from any patient identifiers, such as patient name or medical record number. The record linking the subjects' name with their assigned codes will be kept on the computer in a separate secure folder. All files are password protected on a secure server.

Data Analysis Plan Including Any Statistical Procedures

Continuous variables will be analyzed using two tailed T-test and categorical variables will be analyzed using Pearson Chi Square test. Logistic regression will be used to adjust for confounders. A p-value <0.05 will be considered significant.

22. Data - Safety Monitoring

More Than the Minimum Data Safety Monitoring Will Be Done No

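### The objective claims equal success in the two arms, but the plan contains only tests of difference and so has no result that could support that claim

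*Combined protocol and SAP*

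**What the plan says.** Section 3 (Summary - Background), Objectives, gives one hypothesis: "patients undergoing ECV with spinal anesthesia will have the same rate of success as those undergoing the procedure without anesthesia initially", where the second group is re-attempted under spinal if the first attempt fails. Under Primary and Secondary Study Endpoints, "The primary outcome will be the success rate of external cephalic version to cephalic presentation".

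Section 10, Expected Direct Benefit to Subjects, says of the deferred-spinal group: "It is unclear if these patients will have the same ECV success rate". The same sentence adds that earlier non-randomized work points towards equal success.

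The analysis plan is three sentences in Section 21, Data Analysis Plan. The first reads "Continuous variables will be analyzed using two tailed T-test and categorical variables will be analyzed using Pearson Chi Square test". The other two are "Logistic regression will be used to adjust for confounders" and "A p-value <0.05 will be considered significant".

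Section 7 gives the sample size ("Total Number of Subjects Needed 100") and supports it by recruitment feasibility alone. Nowhere do the documents give a margin, an equivalence or non-inferiority test, a confidence-interval criterion, an expected success rate, a power figure, or a rule for interpreting p≥0.05.

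**The concern.** A chi-square test, or a test of a logistic regression coefficient, takes no difference as its null hypothesis. A small p-value is evidence against equality. A large one shows only that the data did not exclude equality, and in a small trial that happens often when the arms really differ.

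Under this plan, the only result that could be taken as support for the objective is a non-significant p-value, and that would not be evidence of equal success. The case for deferring the spinal depends on success not being materially worse, so this is the question the trial has to answer. With no rule set in advance, the interpretation of p≥0.05 is left until the data have been seen, and a real deficit could be reported as equality.

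**Working it through.** **Inputs from the documents.** Total N = 100 (Section 7); binary primary outcome (Section 3); chi-square, p<0.05 (Section 21). N = 100 cannot be reproduced, because no success rate, difference, margin or power accompanies it.

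**Assumptions.** 1:1 allocation, so n = 50 per arm; no dropout; success p of 50, 60, 70 or 80% in the better arm. The documents give none of these.

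**1. How often a real deficit is non-significant.** This sums the two binomial probabilities over all outcomes (x₁, x₂) for which the uncorrected chi-square gives p≥0.05.

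| True deficit | 50% | 60% | 70% | 80% |
|---|---|---|---|---|
| 10 points | 0.816 | 0.816 | 0.820 | 0.788 |
| 15 points | 0.657 | 0.655 | 0.656 | 0.607 |
| 20 points | 0.454 | 0.457 | 0.454 | 0.405 |
| 25 points | 0.255 | 0.266 | 0.263 | 0.228 |
| 30 points | 0.105 | 0.124 | 0.124 | 0.105 |

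Non-significance is the likely result for deficits of 10-15 points, but not for 25-30 points.

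**2. An example.** Take 35/50 against 26/50. The difference is 0.70 − 0.52 = 0.18 and the pooled rate is 61/100 = 0.61. Then z = 0.18/√(2 × 0.61 × 0.39/50) = 0.18/0.0975 = 1.85, so p = 0.065. The Newcombe 95% interval is −1 to +35 points. The plan has nothing to say about this result except that it is not significant.

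**3. What identical observed rates would show.** Newcombe 95% limits around a zero difference:
- 25/50 in each arm: ±18.9 points
- 30/50 in each arm: ±18.6 points
- 35/50 in each arm: ±17.5 points
- 40/50 in each arm: ±15.7 points

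The simple formula 1.96 × √(2p(1−p)/50) gives 19.6, 19.2, 18.0 and 15.7 points at p = 50, 60, 70 and 80%. Expected precision is therefore about ±16 to ±20 points.

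**4. Chance of showing equivalence when the arms are truly equal.** Probability that the two-sided 95% Newcombe interval lies wholly inside the margin:

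| Margin | 50% | 60% | 70% | 80% |
|---|---|---|---|---|
| ±10 | 0 | 0 | 0 | 0 |
| ±15 | 0.000 | 0.000 | 0.000 | 0.026 |
| ±20 | 0.080 | 0.099 | 0.230 | 0.414 |
| ±25 | 0.516 | 0.526 | 0.606 | 0.766 |

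**5. Margins that N = 100 could support with 80% power** (normal approximation, arms truly equal):
- Equivalence by 95% interval: (1.96 + 1.2816) × √(2p(1−p)/50) = 32.4, 31.8, 29.7 and 25.9 points.
- Non-inferiority, one-sided 0.025: (1.96 + 0.8416) × √(2p(1−p)/50) = 28.0, 27.4, 25.7 and 22.4 points.

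**6. Size needed for equivalence by 95% interval, 80% power.** n per arm = 2p(1−p)(1.96 + 1.2816)²/margin². At p = 50% and a 20-point margin, this is 0.5 × 10.508/0.04 = 131.4, rounded up to 132. Across the four rates the requirement is 85-132 per arm for ±20 points and 150-234 for ±15 points.

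**The case against.** The objective is one informal sentence in an IRB application. It can be read as naming the null hypothesis of an ordinary two-sided comparison, and the opening summary does describe the aim neutrally, as comparing two approaches. On that reading chi-square is a valid test and can answer the question in one direction. This softens the point but does not remove it: the plan could refute its hypothesis and still never support it, and Section 10 treats equal success as a substantive open question.

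It is also true that no passage says a non-significant result will be reported as equality, and nothing prevents the investigators from reporting arm rates or an interval. The defect is an omission. It is still serious, because it concerns the sole stated objective and the primary outcome.

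The equivalence figures use a 95% interval (0.025 per side). Two one-sided tests at 0.05, equivalent to a 90% interval, are less strict: (1.645 + 1.2816) × √(2p(1−p)/50) gives margins of about 23-29 points at N = 100, with about 69-108 per arm needed for ±20 points and 122-191 for ±15. Even so, 50 per arm is too few for ±20.

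Finally, all success rates and the allocation ratio are assumed. The logical defect needs none of them; they only show its likely size.

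**Conclusion.** The concern holds. The objective asserts equal success, the planned tests can only detect a difference, and nothing in the documents connects a non-significant result to a conclusion. This must be fixed.

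Assuming 50 per arm and better-arm success of 50-80%, a true deficit of 10-15 points would give p≥0.05 in about 61-82% of trials. A non-significant result therefore could not separate equal success from a deficit of that size. Even with truly equal arms, a 95% interval inside ±20 points would occur in at most 41% of trials.

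**What to change.** 1. Reword the objective as estimating the difference in ECV success between immediate spinal and spinal only after a failed attempt. Make the primary result the unadjusted risk difference (Group 1 minus Group 2) with a two-sided 95% confidence interval, by the Newcombe or Miettinen-Nurminen method. The chi-square p-value becomes secondary and the logistic regression supportive.
2. State in the Data Analysis Plan that p≥0.05 will not be interpreted as equal success, and that the expected precision with 100 patients is about ±16 to ±20 points, with the assumptions behind that figure.
3. Keep a claim of equal or not-worse success only if the investigators justify a margin and the interval meets it: both limits for equal, one limit for not worse. If it does not, report the result as inconclusive. The arm is evident from the procedure and the person performing it completes the study form, so the margin should be fixed before any outcome is seen by arm. State the confidence level used.

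Items 1 and 2 cost one paragraph and a reworded objective, with no extra patients. The price is a less favourable claim: at this size the trial would most likely report an estimate with its interval rather than equality. An equivalence claim with 80% power at a margin of 20 points or less would need a larger trial.

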This is a randomized controlled trial assessing the success of external cephalic version (ECV). When patients are noted to be in breech presentation (bottom of baby facing down) at 37 weeks gestation they are encouraged to undergo an ECV procedure (an external rotation done by the obstetrician) which rotates the baby to a cephalic presentation (head facing down) in order to allow for vaginal delivery. Patients who fail this procedure undergo a cesarean section if the baby has still not rotated by the time of delivery. At our institution, this is usually done by giving a tocolytic (relaxant to the uterus) and performing the procedure. In rare cases the patient may be offered spinal anesthesia, particularly when the attempt was unsuccessful without anesthesia and the provider believes that anesthesia will facilitate success or if the patient is not tolerating the procedure due to pain. Randomized control studies and a recent meta-analysis have suggested that spinal anesthesia increases the success rate of ECV significantly and decreases the number of cesarean sections. However, there have been limited studies on using spinal anesthesia only if the procedure fails without it. Our study aims to randomize patients who present for ECV into two groups. Group 1: patients who receive spinal anesthesia immediately and Group 2: patients who receive spinal anesthesia only if the procedure first fails without it. Comparing these two groups is essential in order to optimize ECV procedure protocols with the highest success and least invasive approach.

IF Number

IF1989320

2. Summary - Setup

Funding Has Been Requested / Obtained	No
Application Type	Request to Rely on Mount Sinai IRB
Research Involves	Prospective Study ONLY
Consenting Participants	Yes
Requesting Waiver or Alteration of Informed Consent for Any Procedures	No
Humanitarian Use Device (HUD) Used Exclusively in the Course of Medical Practice	No
Use of an Investigational Device to Evaluate Its Safety or Effectiveness	No
Banking Specimens for Future Research	No
Cancer Research that Requires Approval from the Protocol Review and Monitoring Committee (PRMC)	No
Clinical Trial	Yes

**** A prospective biomedical or behavioral research study of human subjects that is designed to answer specific questions about biomedical or behavioral interventions (drugs, treatments, devices, or new ways of using known drugs, treatments, or devices).***

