The individual subject will be participating in the study for approximately 1-8 hours depending on how long the procedure takes. We will then follow-up their delivery information using labor and deliveries' EMR (Peribirth). The patient will not be contacted at this time. Once delivered they will no longer be part of the study. Delivery usually occurs within 5 weeks of the procedure given that the procedure is only done at 37 weeks or higher.

Duration Anticipated to Enroll All Study Subjects

We will be enrolling study subjects for 2 years.

Estimated Date for the Investigators to Complete This Study Within two years

Procedures for Subjects to Request Withdrawal

Patients can withdraw at anytime and will be aware of that option. We will be conducting an intention-to-treat analysis. If the patient decides to withdraw we will then ask the patient if we can still collect their demographic and delivery data. If they allow this, then they will be included in the analysis and this will be stated in our results once the study is written. No identifiers will be included in the results. If they would like to withdraw completely we will not collect any further data and we will not include them in our analysis.

Procedures for Investigator to Withdraw Subjects

There is no circumstance that the patient will be withdrawn without their consent. There is no anticipated reason that a patient would need to be terminated from the study. If there is any concern that there is risk to the fetus during the procedure, the procedure will be terminated and the patient will still be included in the study. This will then be discussed and explained in our study results.

Participants Will Be Recruited Yes
Recruitment Method(s) Clinical Practice

How Participants Will Be Identified

Each day external cephalic versions are scheduled on labor and delivery. When a patient is noted to be scheduled for a version, once they are admitted and there is no contraindication noted for the participation in the study (for example, they come for a version but are found to be in the cephalic presentation that day) they will be asked if they are willing to participate in a study. If the patient agrees, a member of the research team will approach the patient and discuss the study with the patient.

Who Will Initially Approach Potential Participants Study Personnel

How Research Will Be Introduced to Participants

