There are two procedures possibly being performed. In terms of the ECV, all patients will undergo an ultrasound examination as is necessary to confirm the malpresentation of the fetus and rule out any anomalies that would complicate a vaginal delivery. If found to have malpresentation patients will be placed on a fetal monitor and isotonic solution will be administered via IV. A CBC and type and screen will be drawn and sent. The patient will then be consented for the external cephalic version, as this is the procedure that the patient has come to the hospital for, and will be performed regardless if they participate in the study. After this, they will be asked if they would like to participate in a study. If so, a member of the research team will approach the patient and consent the patient for the study. If the patient consents and is randomized to Group 1, the patient will have a spinal administered by the on call anesthesiologist using standard protocol (intrathecal bupivacaine 7.5 mg). The patient will then be administered 0.25 mg Terbutaline subcutaneously and the ECV will be attempted. Under ultrasound guidance the provider will attempt to lift the breech upward from the pelvis with one hand and guide the head with the other hand to produce a forward roll. If forward roll fails, a backward roll somersault may be attempted. ECV attempt will be abandoned if there is significant fetal bradycardia, discomfort to the patient, or if the procedure cannot be completed easily with these maneuvers. Once attempt is complete, whether successful or not, the patient will be monitored for a minimum of 30 minutes, and will be discharged once they are able to walk, void, and tolerate PO intake, only if fetal and maternal status is reassuring. If the patient is randomized to Group 2, the patient will be administered terbutaline 0.25 mg subcutaneously and the version will be attempted using the same procedure as above. If successful, the patient will be monitored for 30 minutes and discharged if fetal and maternal status is reassuring. If the attempt fails, the patient will be administered spinal anesthesia as above and the same maneuvers will be attempted. Once attempt is complete, whether successful or not, the patient will be monitored for a minimum of 30 minutes, and will be discharged once they are able to walk, void, and tolerate PO intake, only if fetal and maternal status is reassuring.

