Attest that you will follow the Short Form Policy ([insert link]), including the Hospital policy (A3-105 at ISMH and HHC Administrative Policy ADM 30 at Elmhurst/Queens) regarding approved interpreters.

18. Consent - Documents**Consent Documents**

Type	Consent
Name	Consent
Upload	Consent2(unmarked).doc

19. Data - Collection

Health Related Information Will Be Viewed, Recorded, or Generated Yes

Description of Health Information That Will Be Viewed, Recorded, or Generated

Primary outcome data to be collected includes: successful external cephalic version. Other information that will be recorded includes: name, MR #, ultrasound findings, patient pain score (1-10) from procedure, score for ease of performing the procedure, complications from procedure, delivery mode, 5 minute, Apgar score <7, arterial cord pH <7.2, NICU admission. Demographic data will also be collected such as age, race, BMI, parity, and medical disease.

Non-Health Related Information Will Be Viewed or Recorded No

HIV / AIDS Related Information Will Be Viewed or Recorded No

Data That Will Be Viewed, Recorded, or Generated Contains ANY of the Following Directly Identifiable Information Yes

Will Be Viewed Name, Medical Record Number

Will Be Recorded Name, Medical Record Number

Data Collection Sheet

A Data Collection Sheet is required if you are either performing a retrospective review, or your study meets the category of exempt 4 research, or your study meets the category of expedited 5 research. Please upload it here.

Data Collection Source(s) Participant, Medical Chart (Paper or Electronic)

20. Data - HIPAA

Obtaining HIPAA Authorization Yes

How PHI Will Be Protected from Improper Use or Disclosure

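### Does the plan need to name spinal receipt and maternal anesthetic events as outcomes in order to judge which strategy is less invasive?

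*Combined protocol and SAP*

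**What the plan says.** The opening summary of the combined protocol and SAP explains the comparison as a way to reach an approach "with the highest success and least invasive approach". The formal objective in section 3 is narrower: that "patients undergoing ECV with spinal anesthesia will have the same rate of success" as patients who try first without it. Under Expected Direct Benefit in section 10, Group 2 patients "may benefit from not having to undergo an additional procedure (neuraxial anesthesia").

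The endpoints in section 3 are version success (primary), then time to delivery, mode of delivery, discomfort, "adverse events during procedure (ie.fetal bradycardia, emergent cesarean section, abruption") and neonatal outcomes. Section 19 lists, among other items, "patient pain score (1-10) from procedure, score for ease of performing the procedure, complications from procedure, delivery mode".

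Section 12 opens its description with "There are two procedures possibly being performed", meaning the version and the spinal. Every Group 1 patient is to have a spinal. For Group 2, "If the attempt fails, the patient will be administered spinal anesthesia as above". After the procedure, section 9 says "We will then follow-up their delivery information" from the electronic record, without contacting the patient.

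**The concern.** If success turns out similar in the two arms, the choice between strategies rests on what each asks of the patient. Discomfort is a stated endpoint. The number of women spared a spinal, and any harm from the spinal itself, are not named.

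Spinal receipt in Group 2 cannot be worked out from the assigned arm and a single success item, because a Group 2 success may have come before or after a spinal. The adverse-event wording points to the time of the procedure, and its three examples are fetal or obstetric. A reader could therefore fear a report that follows the plan to the letter and is silent on the advantage claimed for Group 2.

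**Working it through.** **1. The lists side by side.** Spinal receipt appears in neither the section 3 endpoints nor the section 19 data items. The same comparison shows that birthweight and time from procedure to delivery are section 3 endpoints but are absent from section 19. Section 19 is worded as an inclusive list, so absence from it does not show that an item goes unrecorded. Procedure-level data go on the study form described in sections 12 and 14, whose fields are not reproduced. The most that can be said is that spinal receipt is not prespecified as an outcome.

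**2. The adverse-event wording.** Section 10 describes abruption as an event reported after version, yet section 3 gives it as an example of an event during the procedure. The phrase is therefore not a strict intraprocedural window. Section 19 records complications from the procedure with no time limit, and section 12 counts the spinal as a procedure. Read together, these passages allow spinal complications to be recorded and reported. Nothing excludes them.

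**3. What naming spinal receipt would add.** The plan gives no figure to reproduce. Assumptions, none of them in the documents: 100 patients split 50/50, full adherence, and 40%, 50% or 60% of Group 2 succeeding without a spinal. Exact (Clopper-Pearson) limits for x of n are the 0.025 quantile of Beta(x, n-x+1) and the 0.975 quantile of Beta(x+1, n-x). The Newcombe interval for the difference D = p1 - p2 uses Wilson limits (l, u):

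- lower = D - sqrt[(p1-l1)^2 + (u2-p2)^2]
- upper = D + sqrt[(u1-p1)^2 + (p2-l2)^2]

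For 50/50 against 30/50, l1 = 0.929, l2 = 0.462 and u2 = 0.724. The lower limit is 0.40 - sqrt(0.071^2 + 0.124^2) = 0.257, and the upper is 0.40 + 0.138 = 0.538.

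| Group 2 spinals | Exact 95% CI | Difference from 50/50 (points) | Newcombe 95% CI |
|---|---|---|---|
| 30/50 | 45.2-73.6% | 40 | 25.7-53.8 |
| 25/50 | 35.5-64.5% | 50 | 34.9-63.4 |
| 20/50 | 26.4-54.8% | 60 | 44.4-72.4 |

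The direction is fixed by design, and Group 1 is 100% by assumption. The only unknown is one proportion in Group 2, which a count describes. It tests no hypothesis in the plan.

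**4. What a harm outcome would add.** With zero events in n exposed, the two-sided 95% upper limit is 1 - 0.025^(1/n). The chance of seeing at least one event of true rate 1% is 1 - 0.99^n.

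| Spinals given | Upper limit after zero events | Chance of seeing a 1% event |
|---|---|---|
| 50 (Group 1) | 7.1% | 39% |
| 30 (Group 2) | 11.6% | 26% |
| 20 (Group 2) | 16.8% | 18% |

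The Group 2 rows follow from the assumptions in step 3. At these numbers a comparison of anesthetic harm between arms would say little.

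**5. A longer window.** Section 9 expects delivery usually within 5 weeks. Counting anesthetic events from the record through delivery would bring in anesthesia given for the delivery itself, including cesareans after a failed version. Without a rule to attribute events to the spinal given for the version, the count would be harder to interpret than the present wording.

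**The case for a change.** The strongest case for a change is that a plan which advertises a less invasive approach should say how invasiveness will be measured. Spinal receipt is not derivable from the listed items. It is also not simply the complement of spinal-free success, because section 3 lets a procedure be stopped at any time. If 25 of 50 Group 2 patients succeed without a spinal and 3 more stop early without one, then 50 - 25 - 3 = 22 receive a spinal, although 25 had a spinal-free success. A late spinal complication has no stated route into the data except the delivery record, and a field on a form does not oblige anyone to report it.

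The textual points are right, and naming the two proportions would be tidy and cheap. That does not make the plan defective. Treatment received, by arm, is ordinary conduct reporting in a trial whose arms differ by that treatment, and Group 2 could hardly be described without saying how many went on to a spinal. On harm, incomplete capture of late events is a real limit, but patients are not contacted after discharge and a list of named complications would not remove it.

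**Conclusion.** No change is needed. The plan leaves unsaid something that analysts of this trial would report as a matter of course, and its safety wording is loose but does not exclude maternal anesthetic events. The less invasive aim is summary language. The stated objective concerns equal success, and neither it, the sample size nor the primary comparison is touched.

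Under the assumptions of 50 per arm, full adherence and 40-60% spinal-free success in Group 2, the unnamed quantity is a difference in spinal use of 40 to 60 points, already known in direction. Extra harm reporting would rest on 20 to 30 exposed Group 2 patients and could only be descriptive. The conclusion takes the unseen study form as neutral evidence. If the form had no field for spinal use, the remedy would be a data-collection detail, and the design and analysis would stand.
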